7. STUDY SUBJECTS AND DEMOGRAPHICS

7.1 Disposition of Subjects and Withdrawals

The number of subjects included in each analysis set (Safety, ITT, and PP) will be presented by treatment group and overall. The number and percentage of subjects in the Safety population, who completed the study treatment period, who discontinued the study prior to the end of treatment and the reason for discontinuation, along with the number who completed the Follow-up Visit will be presented for each treatment group and overall.

7.2 Protocol Violations and Deviations

A list of major protocol deviations that could significantly affect study assessments will be identified. The incidence of major protocol deviations will be presented by treatment group for all randomized subjects if appropriate.

7.3 Demographics and Other Baseline Characteristics

Descriptive summaries of the demographic and other baseline characteristics will be completed for all enrolled subjects in the study population by treatment groups.

Descriptive summaries of demographic and other baseline conditions for each analysis set (ITT and PP) will include:

- Demographics:
 - Age (years)
 - Age category (≤ 6 years, >6 years)
 - Gender (male, female)
 - Race (American Indian or Alaska Native, Asian, Black or African American, Native Hawaiian or Other Pacific Islander, White, Other)
 - Ethnicity (Hispanic or Latino, Not Hispanic or Latino)
 - Region (North America, Europe, Middle East and North Africa, and Oceania)
 - Absolute height (cm)
 - Weight (kg)
 - Body mass index (BMI) (kg/m^2)
 - Mother's height (cm)
 - Father's height (cm)
 - Mid-Parental Height (MPH) SDS
- Medical History (including pre-study height velocity)
- Anti-transglutaminase antibodies
- Results of GH stimulation tests: insulin tolerance test (with cortisol response to hypoglycemia), arginine test, clonidine test, glucagon test (with or without propranolol, with cortisol response), L-dopa test
- Peak GH levels in stimulation tests (≤ 5 ng/mL, >5 ng/mL)
- IGF-1 SDS
- Bone age
- Assessment of adrenal and thyroid status
- Results of karyotype testing
- Results of Brain and Sellar Magnetic Resonance Imaging (MRI)
- Prior Medications

Prior medication: Note that all medications will be coded using the World Health Organization (WHO) Drug Dictionary (Version WHODrug-DDE-B2-201603). The frequency and percentage of all prior medications will be summarized by Anatomical Therapeutic Chemical (ATC) class 2 and ATC class 4 if applicable for all safety population by treatment group.

Prior medication is defined as any medications which have a start date prior to the date of the first administration of the study drug.

Note that medical history will be coded with Medical Dictionary for Regulatory Activities (MedDRA) (Version 19.0). Incidences of findings in medical history will be summarized by system organ class (SOC) and preferred term by treatment group.

8. Efficacy Analysis

It may be necessary to complete additional exploratory analyses after the planned analyses are completed. Full details of additional analyses will be presented in the CSR.

All statistical tests except non-inferiority tests will be based on a 2-sided test at the significance level of 0.05 and 95% confidence intervals, unless otherwise specified. Non-inferiority tests will be based on a one-sided significance level of 0.025.

8.1 Primary Efficacy Variable Analysis

The absolute values and mean change from baseline at each timepoint of the annualized height velocity will be presented by treatment group with descriptive statistics.

The primary endpoint, annualized height velocity at week 52, will be compared between TransCon hGH treatment and daily hGH treatment, by a non-inferiority comparison with a non-inferiority margin of 2.0 cm/year, followed by a test of superiority if non-inferiority is established.

As the primary analysis, an ANCOVA model will be used to analyze annualized height velocity at week 52, after potential multiple imputation as described in [Section 6.1.2](#). The annualized height velocity at week 52 will be included in the model as a response variable. The model will include baseline age, peak GH levels (log transformed) at stimulation test, baseline height SDS – average SDS of parental height as covariates, treatment and gender as factors. The estimates from the 100 fitted models for each of the 100 imputed datasets will be combined to provide an overall estimate of the between treatment group difference with a corresponding confidence interval and a p-value.

For the primary efficacy analysis, a 2-sided 95% confidence interval will be calculated for the difference in least square means between the 2 treatment groups [TransCon hGH treatment minus daily hGH] at Week 52. If the lower confidence bound is >-2.0 cm, non-inferiority is demonstrated in terms of effectiveness. If the lower confidence bound is >0 , superiority is established.

Treatment-by-covariate interaction will be examined as appropriate as part of the analysis model examination.

Height velocity at other post-baseline visits will be analyzed similarly using the same ANCOVA model as described above for the primary efficacy analysis. The same ANCOVA model described above will also be used to analyze observed cases as a sensitivity analysis of the primary analysis.

8.2 Secondary Efficacy Variable Analysis

The absolute values and mean change from baseline at each timepoint of other secondary efficacy endpoints will be presented by treatment group with descriptive statistics. Height velocity SDS will also be summarized. Mixed model for repeated measurement (MMRM) models will be used for the following continuous secondary efficacy endpoints. Missing data will not be imputed before conducting the MMRM model. The MMRM model for height velocity will include baseline age, peak GH levels (log transformed) at stimulation test, baseline height SDS – average SDS of parental height, as covariates, gender as a fixed factor, and subject as a random effect. The MMRM model for all the following continuous variables will include treatment, timepoint, and treatment by timepoint interaction.

- height velocity
- change in height SDS
- serum IGF-1 levels
- serum IGFBP-3 levels
- IGF-1 SDS
- IGFBP-3 SDS

The MMRM model for change in height SDS, IGF-1, IGFBP-3, IGF-1 SDS and IGFBP-3 SDS will include baseline age, peak GH (log transformed), baseline (of the corresponding variable) as covariates, and gender as a factor.

For the patients who are in PK/PD population, the average values from hour 48 and hour 72 at Visit 3 (Week 13) will be considered as the Visit 3 value for IGF-1, IGF-1 SDS, IGFBP-3 and IGFBP-3 SDS, and used in the analyses for Visit 3.

Two sided 95% confidence intervals will be calculated for the difference in least square means between the 2 treatment groups. Change from baseline will be summarized when appropriate as supportive analyses.

The rate of subjects achieving normalization of serum IGF-1 SDS will be calculated by treatment group and visit defined as SDS scores of 0 to 2.0. Additionally, cut points of -2.0 to +2.0 and -1.0 to +2.0 will be assessed. The following IGF-1 SDS variables will be derived:

- Average IGF-1 SDS at visits 3, 4, and 5
- Proportion of subjects achieving normalization of IGF-1 SDS of 0 to 2.0 based on the average IGF-1 SDS at visits 3, 4, and 5

The rates of subjects achieving IGF-1 SDS 0-2.0 will be analyzed by logistic regression adjusting for baseline age and baseline IGF-1 SDS. In case of model convergence issues caused by sparse cells, Fisher's exact test will be carried out instead.

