10.1.1 Screening (Day –42 to –1)

The Screening period will last up to approximately 6 weeks during which clinical data will be collected and investigations will be performed to establish the subject's eligibility for the trial. The following assessments will be performed and appropriate data collected.

- 1) Data on current anthropometric measurements (auxology), (auxology to be performed at each visit by the same, trained, blinded auxologist as far as possible):
 - Absolute HT, measured on a calibrated wall-mounted stadiometer

- Body weight
- 2) Data on parental height, if available:
 - Mother's height
 - Father's height
 - 3) Complete medical history, including a description of pituitary deficiencies, currently and previously taken relevant medications and, when available, pre-screening height measurements to assess growth history
 - 4) Overall health status assessment with complete physical examination and vital signs (blood pressure, heart rate, respiratory rate and body temperature) (subjects should rest for at least 5 minutes before vital sign assessment)
 - 5) Pubertal status assessment (according to Tanner stages) (*Tanner 1976*) (scant pubic hair is compatible with Tanner Stage 1, absent breast or testicular enlargement)
 - 6) 12-lead ECG, local reading (subjects should rest for at least 2 minutes before ECG assessment)
 - 7) Collection of blood for the following laboratory assessments:
 - IGF-1 serum levels
 - Anti-transglutaminase antibodies (results within approximately 6 months prior to Screening may be accepted, the final decision rests with the Medical Expert)
 - Anti-hGH and anti-PEG binding antibodies (the analysis of the anti-hGH and anti-PEG antibodies may only be conducted after randomization and are not required for eligibility verification. These data will be used to support evaluation of postdose antibody detection)
 - Routine safety biochemistry and hematology parameters
 - Other hormone levels: thyroid status (TSH, fT4, and fT3 levels) and morning cortisol
 - Glucose metabolism: fasting insulin, glucose, HbA1c. In case of suspected glucose intolerance, an OGTT should be performed (glucose metabolism parameters can be assessed locally at any time if there is suspicion of impaired glucose tolerance, which may include an OGTT)
 - Lipid status: Total cholesterol, triglycerides, HDL and LDL
 - 8) Stimulation tests:

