3.2 Sample Size and Subject Population

This is a pivotal clinical trial intended to support market approval.

Based on the Phase 2 trial (Protocol ACP-001_CT-004) and similar growth hormone studies published in the literature, and assuming a SD of 3.5 cm/year with a non-inferiority margin of 2.0 cm, a sample size of 147 subjects in the ITT population will be needed to show non-inferiority of TransCon hGH treatment compared to daily hGH with a power of 90%. This sample size calculation is based on a 2:1 randomization and a 1-sided alpha level of 0.025.

A sample size of 150 subjects randomized has been chosen to account for slight imbalances in the randomization due to stratification of randomization. For 150 enrolled subjects, approximately 450 subjects may need to be screened in the trial.

Approximately 150 prepubertal, hGH-treatment naïve children (males and females) with GHD will be included. Subjects will be allocated to 1 of 2 treatment groups in a 2:1 ratio:

- Two thirds of the 150 subjects (approximately 100 subjects) will receive TransCon hGH treatment to obtain an expected 90 per protocol subjects in this cohort
- One third of the 150 subjects (approximately 50 subjects) will receive Genotropin treatment to obtain an expected 45 per protocol subjects in this cohort

4. Analysis and Reporting

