6.1.2.2 Step II: Inference

For each of the 100 imputed datasets, height velocity will be recalculated based on the multiply imputed height values. The primary efficacy analysis will then compare the annualized height velocity at Week 52 between TransCon hGH and Genotropin groups in the ITT population. The data will be analyzed using an analysis of covariance (ANCOVA) model with treatment and gender as factors, baseline age, baseline peak GH levels (log transformed) at stimulation test, and baseline height SDS - average SDS of parental height as covariates.

The sample SAS code for the ANCOVA model can be found below:

```
*****
* Note:                                                                 *
*   AAGE = Baseline age                                               *
*   PEAKGHLG = Peak GH levels (log-transformed) at stimulation test   *
*   DMPHTSDS = Baseline height SDS – average SDS of parental height  *
*   _IMPUTATION_ = Iteration number in the multiple imputation       *
*   TRT01P = Treatment group: Genotropin, TransCon hGH              *
*   SEX = Gender                                                       *
*****

ods output lsmeans=lsm diffs=diff;
proc mixed data = ADEFF;
  by _imputation_;
  class TRT01P(ref='Genotropin') AVISIT SEX;
  model AVAL= AAGE PEAKGHLG DMPHTSDS TRT01P SEX/solution cl;
  lsmeans TRT01P/e diff cl;
  where AVISIT='Week 52' and PARAMCD='HGHTVEL' and ANL01FL='Y' and ITTFL='Y';
run;
```

The estimates from the 100 fitted models for each of the 100 imputed datasets will be combined to provide an overall estimate of the least square mean with a corresponding confidence interval for each treatment group and an overall estimate of the difference in least square means between the two treatment groups and a p-value ([6]). The following pseudo SAS code will be used:

```
proc sort data=lsm;
  by trt01p;
run;
```

```
ods output ParameterEstimates=miest_lsm;
proc mianalyze data=lsm;
  by trt01p;
  modeleffects estimate;
  stderr stderr;
run;
```

```
ods output ParameterEstimates=miest_diff;
proc mianalyze data=diff;
  modeleffects estimate;
  stderr stderr;
run;
```

The primary analysis model with ANCOVA will be repeated in the PP population. Because the PP population excludes subjects who have missing data at Week 52, the multiple imputation method described above will not be used for the PP analysis.

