6.1.3 Visit Windows

Table 2: Bioanalytical Samples visit windows from Visits 1 to 6

Visit	Time Relative to Dosing, by Visits (Hours)					
	1	2	3	4	5	6
TransCon hGH	predose, morning	predose, morning	48-72h, morning	48-72h, morning	48-72h, morning	164-172h, morning
Week	1	5	13 (+2)	26 (±1)	39 (±1)	52 (+1)
Day	1	29	87-88	178-179	269-270	365
Genotropin	predose, 2h, morning	morning	morning	morning	morning	morning
Week	1	5	13 (+2)	26 (±1)	39 (±1)	52 (+1)
Day	1	29-35	85-91	176-182	267-273	365

Abbreviation: hGH=human Growth Hormone

TransCon hGH Cohort (Cohort 1)

- Visits 1 and 2 will be performed on the day of the 1st and 5th dosing (Days 1 and 29), respectively.
- Visits 3, 4 and 5 will be performed 48-72 hours after the 13th, 26th and 39th dose, respectively.
- Visit 6 will be performed 7 days after the last dose (Day 365).

All attempts should be made to adhere to the planned visit schedule as specified per [Table 2](#). However, in case the subject is not able to attend Visits 3, 4, 5 and 6 during Week 13, 26, 39 or 52, respectively, these visits can be performed with a + 2 week window for Visit 3, meaning either Week 14 or 15, if Week 13 is not achievable; and a ± 1 week window for Visits 4, and 5, meaning either Week 25 or 27, if Week 26 is not achievable or Week 38 or 40, if Week 39 is not achievable; and a + 1 week visit window for Visit 6, meaning Week 53, if Week 52 is not achievable.

Genotropin Cohort (Cohort 2)

- At Visit 1, subjects will be dosed in the morning at the clinic.
- All subjects in the Genotropin cohort will attend Visit 1 fasting with administration of the dose at the investigational site and predose sampling and will have an additional postdose sampling for hGH at 2 hours.
- Visits 2, 3, 4 and 5 will be performed on any day during Weeks 5, 13, 26 and 39, respectively. Preferably, all clinic visits will be in the morning for consistency of auxology measurements. Visit 4 needs to be conducted in the morning hours, since the subject is requested to be fasting. Visit 6 will be performed 1 day after the last dosing (Day 365) in the morning hours, since the subject is requested to be fasting.

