6.2 Derived and Computed Variables

The following derived and computed variables have been initially identified as important for the analysis of the safety, efficacy or PK/PD as appropriate. It is expected that additional variables will be required. The SAP will not be amended for additional variables that are not related to the primary target or key secondary target variables. Any additional derived or computed variables will be identified and documented in the SAS programs that create the analysis files.

Parameter	Description of Parameter
Date of Birth	Day of 15 is used to impute the day for all birth date
Age (Years)	$(\text{Date of Measurement} - \text{Date of Birth}) / 365.25$
Age (Months)	$((\text{Date of Measurement} - \text{Date of Birth}) / 365.25) * 12$
C _{max}	The maximum serum concentration observed.
Annualized Height Velocity at visit x (HV) cm/year	$[(\text{HT}(\text{Visit } x) - \text{HT}(\text{Visit } 1))] * 365 / [(\text{Date}(\text{Visit } x) - \text{Date}(\text{Visit } 1))]$
Change from baseline over 52 weeks	The value of each variable at each post-baseline timepoint minus the baseline score. The change from baseline will be calculated for: 
 • change in height (HT) SDS • change in serum IGF-1 • change in serum IGFBP-3 • change in IGF-1 SDS • change in IGFBP-3 SDS
Normalized serum IGF-1 SDS	Proportion of subjects with IGF-1 Standard Deviation Score (SDS) of 0 to +2.0. Also derive for -2.0 to +2.0, -1.0 to +2.0.

Parameter	Description of Parameter
Total duration of treatment (day)	
TransCon hGH Last dose date – first dose date + 7
 
Genotropin Last dose date – first dose date + 1

Total number of planned doses	
TransCon hGH Round (Last dose date – first dose date + 7)/7 to the nearest integer
 
Genotropin Last dose date – first dose date + 1

Total Actual Dosage (mg)	
TransCon hGH Sum Concentration (mg/mL) x volume (mL) over all injections
 
Genotropin Sum dose (mg) over all injections

Parents' Height SDS	
$((\text{Parents Height}/M)^L - 1)/(L \times S)$
 
Where M=median , S= generalized coefficient of variation, and L= power in the Box-Cox transformation, the M, S, L values are obtained from the CDC website; Percentile Data Files with LMS Values

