8.6 Multiplicity Analysis/Procedure

The familywise type-1 error of the study is controlled at 2-sided $\alpha = 0.05$. Non-inferiority for AHV will be tested first, based on the primary analysis (method as described in [Section 8.1](#)). If successful, then the superiority for AHV will be tested next.

9. Safety and Tolerability Analysis

The analysis of safety assessments will include summaries of the following categories of safety and tolerability data collected for each subject and will use the safety analysis set:

Adverse Events

- Adverse Events (AEs), treatment-emergent AEs (TEAEs), and serious adverse events (SAEs)
- AEs leading to withdrawal
- Any deaths

Clinical Laboratory Investigations (Biochemistry, Hematology, Hormone Levels, Glucose Metabolism, Lipid Metabolism, Antibodies)

Vital Signs (blood pressure, heart rate, respiratory rate, body temperature)

Electrocardiograms (ECG)

Physical Examinations

Concomitant Medications

Study Drug Exposure

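### As written, the height-velocity MMRM in SAP 8.2 imposes one variance on all visits, although annualizing multiplies height gain by about 13 at Week 5 and by 1 at Week 52

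*SAP*

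**What the plan says.** SAP 8.2 analyses height velocity over the visits with an MMRM. The fixed part has age, log peak GH, the child-minus-parental height SDS difference, gender, treatment, visit and treatment by visit. The only within-subject term is in the phrase "gender as a fixed factor, and subject as a random effect". Neither document names a residual covariance structure, a REPEATED term or visit-specific variances. The only model code in the SAP, in 6.1.2.2, is "model AVAL= AAGE PEAKGHLG DMPHTSDS TRT01P SEX/solution cl". That is the Week 52 ANCOVA, which has neither a RANDOM nor a REPEATED statement, so it does not settle the question.

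The response is defined in SAP 6.2 as "Annualized Height Velocity at visit x (HV) cm/year": height gain since Visit 1, times 365, divided by the days since Visit 1.

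Table 14.2.1.3 will report this MMRM. Separately, SAP 8.1 states "Height velocity at other post-baseline visits will be analyzed similarly using the same ANCOVA model" (Table 14.2.1.8). The confirmatory sequence in SAP 8.6 is "Non-inferiority for AHV will be tested first, based on the primary analysis", followed by superiority; both rest on the Week 52 ANCOVA.

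**The concern.** A random subject intercept with independent residuals gives every visit the variance (between-subject + residual) and every pair of visits the same covariance. The treatment-by-visit term frees the means but not the variances.

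The endpoint's definition works against a common variance. A given error in a height reading counts about thirteen times as much in the Week 5 velocity as in the Week 52 velocity. A model that averages the visit variances then gives intervals that are too narrow where the variance is high and too wide where it is low. At stake are the 95% intervals for a listed secondary endpoint, annualized height velocity over 52 weeks. The MMRM sensitivity table 14.2.1.7 would be affected too if it uses the same model.

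**Working it through.** **The plan's own figure.** SAP 3.2 plans the trial "assuming a SD of 3.5 cm/year", with margin 2.0 cm, 90% power, one-sided 0.025 and 2:1 allocation. Control n = (1.960 + 1.282)² × 3.5² × 1.5 / 2.0² = 48.3, so 49, plus 98 on TransCon hGH = 147, as stated. I therefore take 3.5 cm/year as the Week 52 SD.

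**Scaling factors** (SAP 6.2 with the days in SAP Table 2, counted from Visit 1). For TransCon hGH:

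| Visit | Days | 365/days |
|---|---|---|
| Week 5 | 28 | 13.04 |
| Week 13 | 86.5 | 4.22 |
| Week 26 | 177.5 | 2.06 |
| Week 39 | 268.5 | 1.36 |
| Week 52 | 364 | 1.00 |

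For Genotropin, "Visits 2, 3, 4 and 5 will be performed on any day during Weeks 5, 13, 26 and 39, respectively", so the Week 5 factor runs from 365/34 = 10.7 to 365/28 = 13.0.

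**Assumptions not in the documents.** The height-measurement SD (me) is taken as 0.1, 0.2, 0.3 or 0.5 cm per reading. Protocol 10.1.1 specifies "Absolute HT, measured on a calibrated wall-mounted stadiometer" but gives no error figure. Two patterns for the SD of true velocity are used:
- (A) constant over visits;
- (B) rising linearly in days from 0.57 of its Week 52 value at Week 5 to 1 at Week 52.

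Subjects: 100 v 50, complete data.

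**Formulas.**
- Visit variance = (f × sdb)² + 2 × me² × (365/days)², where f is the pattern above and sdb is set so that the Week 52 SD is 3.5.
- Compound-symmetry SE = √[mean of the five visit variances, pooled over arms × (1/100 + 1/50)].
- True SE = √(vT/100 + vG/50), where vT and vG are the visit variances on TransCon hGH and Genotropin.
- Coverage = 2Φ(1.96 × ratio) − 1, where ratio = model SE / true SE.

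**Worked case: (A), me = 0.3 cm.**
- sdb² = 12.25 − 2 × 0.09 × 1.0055 = 12.07.
- Week 5, TransCon hGH: 12.07 + 0.18 × 13.04² = 42.66, SD 6.53.
- Week 5, Genotropin: the mean of (365/days)² over 28–34 days is 365²/(28 × 34) = 139.9, so 12.07 + 0.18 × 139.9 = 37.26.
- Pooled variances at the five visits: 40.87, 15.26, 12.83, 12.40, 12.25; mean 18.72.
- Model SE at every visit: √(18.72 × 0.03) = 0.749.
- True SE at Week 5: √(0.4266 + 0.7452) = 1.082. Ratio 0.69, coverage 82%.
- True SE at Week 52: √(12.25 × 0.03) = 0.606. Ratio 1.24.

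**All settings.**

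| Measurement SD (cm) | 0.1 | 0.2 | 0.3 | 0.5 |
|---|---|---|---|---|
| (A) Week 5 SD, TransCon hGH | 3.95 | 5.08 | 6.53 | 9.83 |
| (A) Week 5 ratio | 0.92 | 0.79 | 0.69 | 0.59 |
| (A) Week 5 coverage | 93% | 88% | 82% | 75% |
| (A) Week 52 ratio | 1.03 | 1.11 | 1.24 | 1.57 |
| (B) Week 5 ratio | 1.09 | 0.81 | 0.68 | 0.57 |
| (B) Week 5 coverage | 97% | 89% | 81% | 74% |
| (B) Week 52 ratio | 0.82 | 0.93 | 1.07 | 1.45 |
| (B) Week 52 coverage | 89% | 93% | 97% | >99% |

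**Where the direction changes (linear rise).** Let r be the Week 5 true-velocity SD as a fraction of that at Week 52.
- The Week 5 interval becomes too wide only at 0.1 cm with r below 0.77. At 0.2 cm or more it is always too narrow.
- The Week 52 interval becomes too narrow for r below 0.94, 0.76 or 0.31 at 0.1, 0.2 or 0.3 cm, and never at 0.4 cm or more.
- At 0.1 cm with r = 0.9, all five SEs are within 5% of correct.

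**Simulation check** (4,000 trials per setting, REML compound symmetry, Satterthwaite degrees of freedom). Week 5 coverage was 93.1/88.1/82.2/75.5% in (A) and 96.8/88.8/82.2/74.6% in (B). A separate variance per visit gave 94.9–96.3% at Week 5 in the same trials.

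**The case against.** The strongest reply is that the SAP calls the model an MMRM, a label that often implies an unstructured covariance, and that compound symmetry follows only if the subject effect is read as the whole within-subject model with default residuals. For the other five MMRMs in 8.2 no within-subject term is stated at all, which suggests that the paragraph lists covariates and leaves covariance open. This shows that an unstructured matrix may be intended. It does not rescue the sentence: the one term given for height velocity is a random effect, and nothing says that anything else accompanies it. If unstructured is meant, the text still needs the correction.

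Second, the size rests on a measurement error that cannot be seen. The protocol's appendix on obtaining height measurements is redacted and might require repeated readings, which would lower the effective error. The 0.57 starting point in (B) is also only an illustration. This stands: no particular interval can be shown to be wrong from the documents, and at 0.1 cm the effect is small in (A). On the other hand, 3.5 cm/year is a planning SD. If covariate adjustment left a smaller residual SD, the distortion would grow: with 2.0 cm/year in (A), the Week 5 ratio is 0.82 at 0.1 cm and 0.58 at 0.3 cm.

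Third, no confirmatory claim depends on this model, and the by-visit ANCOVA supplies intervals that do not use this covariance. That is correct and limits the weight of the point. It also means that two planned tables could show much the same visit differences with different interval widths.

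**Conclusion.** The concern holds. Fitted as written, the height-velocity MMRM has a single variance across visits, and the endpoint's own definition makes that implausible unless measurement error is small or roughly offset by a trend in true-velocity SD. Under the stated assumptions, Week 5 coverage of the nominal 95% interval ranges from 97% down to 74%, and the Week 52 SE ranges from 18% too small to 57% too large. The direction at Week 52 is not determined by the documents. The effect is confined to the secondary MMRM intervals for height velocity. The sample size, the non-inferiority and superiority tests and the by-visit ANCOVA stand. It should be corrected, but it does not threaten the trial's main conclusion.

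**What to change.** In SAP 8.2, replace the subject random effect with wording such as:

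> An unstructured within-subject covariance across visits will be used (REPEATED AVISIT / SUBJECT=SUBJID TYPE=UN), with Kenward-Roger degrees of freedom. If the model does not converge, heterogeneous Toeplitz and then heterogeneous compound symmetry will be used, so that each visit keeps its own variance.

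The essential part is a separate variance at each visit, which is suitable whatever the measurement error turns out to be. The degrees-of-freedom method and the fallback order are conventional choices; naming them in advance avoids choosing after the results are seen. Stating the same structure for the other five MMRMs would be a clarification for consistency, since no error is shown for them.

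The cost is one sentence and one line of code. An unstructured matrix over five visits has 5 × 6 / 2 = 15 parameters, which is negligible for about 150 subjects, of whom the SAP's document history reports only two early discontinuations.
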